10. Number of the subjects that will be recruited for study

At least seventy dyads (i.e. 70 veterans and 70 caregivers) will be recruited to achieve a final sample. However, caregivers can participate independently if the veteran is too impaired to participate meaningfully in the study.

11. Subject inclusion/selection criteria

Veterans:

- a. Must be age 19 or older
- b. Must have a diagnosis of dementia or a related disorder
- c. Must live in the community (i.e. not in a VA Community Living Center, nursing home, or other facility)
- d. Must cohabitatem with a caregiver;
- e. Must have reliable access to a telephone
- f. Must be willing to consent to participate or provide assent in conjunction with proxy consent if their decision-making capacity is compromised.

Caregivers:

- a. Must be age 19 or older
- b. Must self-identify as assisting with care for at least 8 hours/week
- c. Must be willing to consent to participate.

The study will include women and minorities and aim to represent the percentage reflected in Tuscaloosa VAMC medical care system (12% women, 44% minorities, and 1% Hispanic origin; though numbers of minorities might be slightly lower in the older cohorts targeted for this study as indicated above). No specific inclusion/exclusion criteria related to race/ethnicity are required.

12. Subject exclusion criteria

In addition to meeting the inclusion criteria outlined above, participants will be excluded in the following cases.

Veterans:

- a. Currently incarcerated
- b. Currently pregnant
- c. Dyads experiencing low levels of distress (as defined by a score of 0 or 1 on the Dementia Services Mini-Screen³², see below)

Note. Baseline or post-assessment interviews will be discontinued for Veterans experiencing severe cognitive impairment that would impair their ability to communicate during an interview, consistent with good clinical practices. However, they will not be excluded from participating in intervention sessions as appropriate and their available data (self-report or proxy report) will be retained for analyses.

Caregivers:

- a. Currently incarcerated
- b. Currently pregnant
- c. Experiencing severe cognitive impairment that would impair their ability to communicate during an interview
- d. Dyads experiencing low levels of distress (as defined by a score of 0 or 1 on the Dementia Services Mini-Screen³², see below)

13. Subject exit criteria

- a. Subjects will exit the study once one of the following conditions are met:

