- b. Completion of the study protocol
- c. Serious or life threatening adverse effects (including death)
- d. Withdrawal of consent by the Veteran or the Veteran's caregiver

14. Justification for use of special subject populations who may present informed consent issues (for example, incompetent patients, children, elderly, etc.) and reason for inclusion.

The study will not enroll prisoners, children, those who are terminally ill, or pregnant women. The study sample will include participants with varying degrees of cognitive impairment (from intact to severely impaired) and other mental health diagnoses (e.g., serious mental illness) that would classify them as vulnerable populations. In the event that these participants have impaired decision-making capacity, appropriate surrogate

consent will be obtained as described below. This vulnerable population is necessary to include in the current feasibility study to examine whether the intervention will ultimately be beneficial for this principal group. It is also possible that veterans over the age of 89 will be included in this research. However, veterans over the age of 89 will not be specifically targeted for enrollment.

15. Scientific and ethical justification for excluding classes (gender, race, etc.) of persons who might benefit from the research

No participant will be excluded from participation in the study on the basis of gender, race, ethnicity, socio-economic status, or physical disability.

16. Appropriateness of Impact of Study design on risk.

The risk of this study is low to minimal since it does not involve study medication or invasive procedures. Furthermore, all participants will receive an active treatment / intervention.

Minimal risks for veterans and their family members include:

- a. they may feel coerced to participate in interviews,
- b. they may feel uncomfortable, tired, or become bored during interviews,
- c. raw data from interviews may contain sensitive information that could cause embarrassment if it was obtained by others in an identifiable form.

It is unlikely that any discomfort or negative emotions will exceed those encountered as part of daily life. Interviews will be conducted separately for the veteran and their family member unless the veteran requests otherwise to increase privacy and minimize risk of embarrassment or discomfort. Given the benefits possible and minimal risks involved, the risk-benefit ratio for this study is favorable.

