17. Description of procedures to be performed.

The assessment schedule is summarized in Table 1 for screening (phone), baseline (in-person), 6-month assessment visit (in-person), and 12-month (phone) assessments. However, if a dyad prefers to complete the telephone assessments in person (e.g., while they are on station for another appointment), arrangements will be made to accommodate that request.

Table 1. Assessment Schedule

Measure (completed by Veteran or caregiver)	Admin. Time	S	B	6 mo	12 mo
Eligibility Screening (CG)	5m	X			
Dem Serv Mini-Screen (CG)	< 2m	X			
Subjective Stress/ Subjective Health (V, CG)	1m		X	X	X
Demographics (CG, CG*)	< 10m		X		
Health Literacy Screener (CG)	< 2m		X		
MoCA (V)	10m		X		

PSM IADL/ADL (CG*)	10-12m		X		
RMBPC (CG*)	5-10m		X	X	
CSDD (V, CG*)	10-20m		X	X	
Veteran QOL-AD (V, CG*)	5-10m		X	X	X
EuroQoL-5 Domain (V, CG*)	<5m		X	X	
Social Engagement (V, CG*)	<5m		X	X	
Dyadic Adj. Scale (V, CG)	5-10m		X	X	
Mutuality Scale (V, CG)	5m		X	X	X
Zarit Burden (CG)	< 5m		X	X	X
GAD-7 (CG)	< 5m		X	X	X
CES-D (CG)	5m		X	X	X
WHO-QOL-OLD (CG)	3m		X	X	
FFMQ (V, CG)	10m		X	X	X
Desire to Inst. (DTI) (CG)	<5m		X	X	X
NH Placement (EHR, CG)	<1m			X	X
Care Consultation Satisfaction Survey (CG)	<5m			X	
Caregiver Time Burden (min)			<130	<105	<50
Veteran Time Burden (min)			<80	<75	<30

Note. V = measures completed by veteran; CG = completed by caregiver; EHR = extracted from the electronic health record.

Screening

A HIPAA waiver for screening purposes will be obtained. Eligibility screening for interested dyads will typically occur over the telephone. If the Veteran and/or caregiver meets the inclusion criteria and do not meet exclusion criteria, a baseline assessment appointment will be scheduled. Informed consent procedures will be performed at baseline in accordance with the consensus recommendations for research with cognitively impaired populations developed by the Alzheimer's Association³³ and described in detail below. Proxy consent and participant assent will be collected when the participant is willing to assent for the study but is determined by the capacity assessment at the time of consent to be lacking capacity. Caregivers will also complete an informed consent. Veterans and their family caregivers will complete separate consent forms.

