r. The 6-item **Desire to Institutionalize (DTI)** Scale⁵¹, which assesses the caregivers planning, thoughts, and actions about long-term care (LTC) placement over the past 6 months will be used to assess intentions to institutionalize their loved one. Six yes/no items (e.g., taken steps toward placement) are summed for a score of 0-6. Long-term care placement and/or hospitalization of the veteran (institutionalization) will be assessed using a single item rated either by the caregiver or via electronic health record review if the dyad is no longer enrolled in the study (e.g., due to attrition).

s. The 21-item **Care Consultation Satisfaction Survey** will be used to measure the participants' satisfaction with the Care Consultant and the Care Consultation services provided.

Once baseline data are collected, dyads will be randomly assigned to a condition (see interventions delivered below).

Randomization

Blocked randomization stratified by race and gender will be used to assign participants to either the: (a) CC group, or the (b) CC+C group. This two-group experimental design was chosen over other approaches (e.g., no comparison group designs, three-group design, cross-over design, etc.) because it most closely approximates the next level of clinical research (e.g., an efficacy study), which allows for the most directly applicable conclusions.

Interventions Delivered

1. Care Consultation (CC): is an established telephone-based, empowerment intervention that uses coaching and emotional support to mobilize family caregivers and individuals with dementia through psychoeducation, resource referral, psychosocial support, and encouragement of informal and formal service use utilization. A computerized clinical tool utilizing a password-protected VA-hosted website (i.e., operated within the VA server system) called the Care Consultation Information System (CCIS) guides the care consultant through a standardized delivery of protocol components, replacing a paper-based clinicians manual. Rather than a strong focus on assessment, this intervention is designed to quickly identify areas of unmet need through brief trigger questions called the “initial assessment” – much like an interview guide – which then immediately shapes development of concrete action plans.

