disability payments. When persons with impaired decision-making capacity are included, surrogate consent will be obtained (described below). Including persons with impaired decision-making capacity as participants is essential in this study and will allow us to gain an understanding of quality of care needs for this population of veterans. In the case of compromised capacity, legally authorized representatives will be able to complete proxy consent procedures. Specifically, the participants' legally authorized representatives (LAR) will receive details about the research study. Participant assent (i.e., patient's willingness to take part in the study) will also be required for their involvement and noted in the source documentation. Note, however, that caregivers can participate without the veteran when that is consistent with the wishes of a given family or the veteran is too impaired to participate meaningfully. Subsequently, the participant's original informed consent documents will be maintained with other essential documents.

Location of the consent process: A private setting, such as TVAMC office or in the participants' home or private room in a community setting (library or veteran service office).

Who will conduct consent: A qualified IRB-approved member of the research team will be responsible for explaining the study, answering questions, and obtaining informed consent. All individuals completing the consent procedure for the research team will have extensive training on the informed consent process and their training will be approved by the PI prior to any procedures being performed.

Decision-making Capacity of the Potential Volunteer: Participants who provide their own consent must have decision-making capacity at the time of the consent discussion and assessment visit. Members of the investigative team have prior experience conducting research with individuals with impaired decision-making capacity; the person obtaining consent will be thoroughly trained using IRB-approved procedures to ensure decision-making capacity before consenting participants. Under all circumstances, the participant's autonomy will be respected. Specifically, the following protocol has been used in the PI's prior research with individuals with dementia:

Capacity Protocol

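### Section 13 ends study participation, not only sessions, after a non-fatal serious adverse effect and does not say whether the partner stays, so scheduled 6- and 12-month outcomes go uncollected

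*Combined protocol and SAP*

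**What the plan says.** Section 13 opens with "Subjects will exit the study once one of the following conditions are met". Besides completion of the protocol, the conditions are "Serious or life threatening adverse effects (including death" and "Withdrawal of consent by the Veteran or the Veteran's caregiver". What ends is participation in the study. The section does not treat sessions and assessments separately.

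Section 17, measure r, gives one route to data after exit: placement and/or hospitalization may be obtained "via electronic health record review if the dyad is no longer enrolled in the study (e.g., due to attrition". No other measure in Section 17 has such a route.

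Several places bear on the partner of someone who exits. Section 17 (Screening) says "Veterans and their family caregivers will complete separate consent forms". Section 23 adds that "caregivers can participate without the veteran when that is consistent with the wishes of a given family", and Section 10 allows the same when the veteran is too impaired. The note in Section 12 does separate interviews, sessions and data retention, but only for veterans with severe cognitive impairment.

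Section 20 (Treatment of Missing Values) limits the final analyses to people with at least four sessions and available 6-month data. It sets strict intention-to-treat aside and allows list-wise deletion. It also says that any relation of missingness to group or outcome will be examined and, if necessary, controlled for.

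**The concern.** A serious adverse effect is a reason to ask whether sessions should go on. It is not in itself a reason to stop measuring outcomes. As worded, the rule does both, so a living participant who still consents would have no 6- or 12-month assessment. The rule is also silent on the other member of the dyad, so staff could handle similar dyads differently.

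This matters because the caregiver supplies much of the outcome data: burden, anxiety, depressive symptoms and desire to institutionalize, as well as ratings of the veteran's behavior, depression, quality of life and social engagement. Losing a willing caregiver therefore also loses the veteran's proxy outcomes. If exits are related to outcome and differ by arm, the 6-month comparison is distorted. Adjustment for missingness cannot restore outcomes that were never collected. A difference by arm is possible, since CC+C adds counseling modules and puts its focus on sequential sessions with both members, but the documents do not show one.

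**Working it through.** **1. The plan's own figure.** Section 20 recruits 70 dyads for 50 completers at 6 months. The implied loss is 1 − 50/70 = 28.6%, or 20 dyads. Going back, 50/(1 − 0.286) = 70, which is circular because no dropout rate is stated. The figure does not show whether exits under Section 13 were counted.

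**2. What is lost at exit.** Table 1 marks 16 rows at 6 months and 9 at 12 months. Only the placement row survives exit, through measure r. That leaves 16 − 1 = 15 rows at 6 months and 9 − 1 = 8 at 12 months without a route. Each of those rows names the caregiver as a respondent, alone or with the veteran.

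**3. Whether the partner must leave.**
- Towards both leaving: the withdrawal condition names either member, and measure r speaks of the dyad as the unit no longer enrolled.
- Towards the partner staying: Section 13 speaks of subjects, Section 9 describes two groups of participants, Section 10 counts 70 veterans and 70 caregivers, consent forms are separate, and Sections 10 and 23 let caregivers take part alone.

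The weight is on the partner staying, but no sentence says so.

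**4. Possible bias.** Let f1 and f2 be the proportions exiting in the two arms. Let D be the gap in SD units between those who exit and those who stay, taken as equal in both arms. Leaving out the exits shifts each arm's mean by f × D, so the arm difference is biased by (f1 − f2) × D. All rates and gaps below are assumptions.

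| Exit rates by arm | D = 0.5 SD | D = 1.0 SD |
|---|---|---|
| 5% and 5% | 0 | 0 |
| 10% and 5% | 0.025 SD | 0.05 SD |
| 15% and 5% | 0.05 SD | 0.10 SD |
| 20% and 10% | 0.05 SD | 0.10 SD |

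For scale, Section 19's neighbor in the analysis text, the effect-size paragraph of Section 20, treats partial eta squared of .01 as potentially meaningful. With equal arms that is d = 2 × √(0.01/0.99) = 0.20. D has to be the gap that remains after baseline adjustment, because the analysis is ANCOVA.

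**5. Possible loss of numbers.** If the rule removed a further 5%, 10% or 15% of the 70 dyads beyond the 20 implied losses, completers would be 50 − 3.5 = 46.5, 50 − 7 = 43 or 50 − 10.5 = 39.5. If these exits are already among the 20, the count stays at 50, though bias remains possible.

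**The case against.** The strongest reply is that little of this loss can be recovered. Rewording cannot bring back data after a participant's death or full withdrawal of consent. After a veteran's death, desire to institutionalize has no object, and burden and mutuality no longer measure the same thing. Section 16 rates the risk as low to minimal, and Section 22 does not expect serious adverse reactions. Section 20 already promises to look at missingness related to group or outcome. The four-session rule would exclude anyone who stops earlier, even if assessed at 6 months. The consent forms are not in the public file and may say how data are handled after withdrawal.

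Most of this stands and limits the point to two groups: people with a non-fatal serious adverse effect, and partners of someone who withdraws or has such an event. It does not remove the point. Low expected numbers do not justify ending assessments for those affected, and Section 13 does not say whether an adverse effect must be caused by the study to count.

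A reader might infer that Section 13 forces a consenting caregiver out when the veteran withdraws, and so contradicts Section 23. That is one reading of an ambiguous line, and the separate consents and the provisions for caregivers taking part alone point against it. A reader might also infer a contradiction with Section 17. Measure r supplements the exit rule: it preserves one outcome after exit. What it leaves open is whether record review applies once consent has been withdrawn.

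**Conclusion.** The point holds in a limited form and is worth correcting. Section 13 ends assessment along with sessions after a non-fatal serious adverse effect, and leaves the partner's position open. Apart from placement or hospitalization, the 6- and 12-month outcomes of these cases would not be collected, and Section 20 would drop them from the 6-month analyses.

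The documents give no rates of events or withdrawals, so neither the size nor the direction of bias can be computed. It is zero with equal exits and equal deficits. It reaches 0.05 to 0.10 SD only under an assumed 10-point difference in exit rate and an assumed gap of 0.5 to 1.0 SD.

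Two stronger conclusions are tempting. One is that a definite number of caregivers is lost, such as 7 to 14 (10% to 20% of 70). Those rates are not in the documents, and the count would mix in deaths and caregivers' own withdrawals, which cannot be recovered. The other is that the rule removes the worst-off. That is a reasonable inference for serious adverse effects, but the documents do not show it for withdrawal of consent.

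**What to change.** In Section 13, separate stopping intervention sessions from leaving follow-up, and leave the rule on sessions as it is. Then state:

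- that the scheduled 6- and 12-month assessments continue for any living member who has not withdrawn their own consent to data collection;
- that one member's withdrawal or event does not end the partner's assessments;
- whether record review of placement and hospitalization applies after consent is withdrawn.

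Reconcile Sections 13, 17 (measure r), 20 and 23 with this. Section 20 needs attention of its own: unless its four-session rule changes, people who stop before the fourth session stay out of the analysis even when their 6-month data exist.

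The assessments are already in Table 1. The cost is protocol and consent wording and a small number of extra 6-month visits, which are in person and need staff travel; the 12-month assessment is by telephone.

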Participants assigned to both groups will have: 1) reduced unmet needs, 2) reduced depressive symptoms, and 3) higher levels of satisfaction with care at 6 months than their baseline assessment values.

Caregivers assigned to CC+C will have greater reductions in caregiver burden at 6 months than those assigned to CC alone. Indicators of relationship strain (e.g., marital distress and/or mutuality) will show greater improvement in CC+C than CC at 6 months. 6 month gains in shared pleasant events, social engagement, and quality of life will also be greater in CC+C than in CC alone. 6-month desire to institutionalize will be lower in the CC+C group than those randomized to CC. Treatment engagement (e.g. action plan completion, attendance) is also predicted to be higher in the CC+C group than in CC.

For Aim 3, we anticipate that individuals who receive the CC+C intervention will have lower rates of placement in long-term care facilities at 6 and 12 months than those who receive CC alone. We also expect that behavioral problems will impact treatment outcomes such that those dyads with higher levels of behavioral disturbance at baseline will have greater change scores at 6 months. Spousal relationship to the veteran is also expected to moderate treatment outcome such that spousal caregivers are anticipated to have lower change scores compared to non-spousal caregivers across time; however, we expect this effect to be attenuated in the CC+C condition.

7. Background, including results of relevant research, gaps in the current knowledge.

Scope of the Problem

Over five million Americans are diagnosed with Alzheimer's disease or a related disorder (ADRD) and rates are expected to triple by 2050¹. It is the 6th leading cause of death in the United States and one in three older adults will have dementia when they die².

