The Dementia Services Mini-Screen³² will be used to identify dyads who are in distress and most likely to benefit from enhanced dementia services. This brief assessment tool was developed for use in primary care settings and has established cut-off points with strong sensitivity and specificity data that categorize individuals with dementia and their caregivers into low, moderate, or high stress groups based on the presence of behavioral disturbances and service needs (psychosocial and medical). Using this tool, dyads that endorse only low-moderate stress and few behavioral problems (0 or 1) will be excluded from the study. Excluded dyads will be offered a referral for clinical services. There will be no restrictions on gender or race for veterans with dementia or their caregivers.

Baseline, 6-month, and 12-month Assessments

Baseline and 6-month assessments will occur in the participant's homes or another convenient location of their choice (e.g., local public library). Informed consent will be the first thing addressed during the baseline assessment. Patient data will be collected interview-style by a trained assessor (research assistant) for the veteran with dementia, while the caregiver measures will be completed independently (paper and pencil). The brief 12-month assessment will occur over the telephone to reduce participant burden.

Measures

See assessment schedule described in Table 1 above. All measures are peer-reviewed and frequently used in the research literature with the proposed population. One measure that is likely less familiar to the IRB (i.e., Dyadic Adjustment Scale) has been uploaded with the submission package on IRBNet.

- a. **Subjective Health** will be measured using the sum of three items, with higher scores indicating better health.³⁴ **Subjective Stress** will be measured using two items, with higher ratings indicating increasing levels of stress.

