- b. **Demographics** including: sex, age, primary racial or ethnic group, education, living arrangement, time since diagnosis, years married, number of marriages, number of children, and income adequacy will be collected for the veteran and their caregiver. Income adequacy will be assessed with a single item asking about difficulty paying for the basics, (1 = very difficult to 5 = not very difficult). Individuals will be asked if they have had any previous counseling experience, are taking any antidepressants, anxiolytics, or memory enhancers and whether doses have been stable for the past 3 months.
- c. **Health Literacy** will be measured using a 4-item screener to identify individuals with health literacy issues that could impact their ability to complete self-report measures.
57,58
- d. The **Montreal Cognitive Assessment (MoCA)**³⁵ a 30-point cognitive screening instrument with excellent discriminative power to detect mild cognitive deficits will be used to measure cognitive status.
- e. The **Physical Self-Maintenance (PSM) and Instrumental Activities of Daily Living (IADL) Scale**³⁶ will be used to assess functional status or independence in daily care needs across six physical care domains (i.e., activities of daily living, ADL) and eight IADL domains.
- f. The **Revised Memory and Behavior Problems Checklist (RMBPC)**³⁷ which provides an estimate of the frequency of problems and the impact that these problems have on the caregiver will be used to rate behavioral symptoms of dementia.
- g. The **Cornell Scale for Depression in Dementia (CSDD)**³⁸ which relies on an interview with the individual and the caregiver will be used to assess depressive and anxiety symptoms.

- h. The **Quality of Life in Alzheimer's Disease scale (QOL-AD)** will be used to assess quality of life.³⁹ Patients and caregivers rate thirteen domains: physical health, energy, mood, living situation, memory, family, marriage, friends, chores, fun, money, self and life as a whole, using a Likert-type scale.
- i. The **Euro-QoL-5 Domain (EQ-5D)** mobility, selfcare, and usual activities subscales will be used to assess autonomy and functional dependence.⁴⁰ Health-related quality of life is assessed for five domains: mobility, self-care, usual activities, pain/discomfort and anxiety/depression. Caregivers also complete this measure, as has been done in previous studies with individuals with mild to moderate dementia.^{40,41,42}

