Treatment delivery: The MSW-level interventionist will be trained to criterion and will be certified before administering the intervention. Accuracy of treatment delivery will be monitored. The interventionist will also complete a fidelity checklist to ensure that all treatment components are delivered during each session. As one measure of potential bias, the treatment fidelity checklist will include a self-reported item assessing the interventionists' desire/pressure to alter the randomly assigned condition for each dyad (i.e., agreement with the following statement will be assessed: "I believe the other arm of the study would have been a better fit for this dyad than the one they were randomly assigned"). Sessions will be audiotaped and 30% of sessions will be randomly selected and reviewed to ensure treatment fidelity to the CC and CC+C protocols. Treatment receipt: will be assessed by documenting the length of all intervention sessions (i.e., direct time spent with the dyads) and indirect time (e.g., documentation, case management, etc.). Participant knowledge of interventions components, which is sometimes included in measures of treatment receipt, is not appropriate for this study.¹¹⁰ Treatment enactment: will be monitored by: 1) the number of completed Action Plans and homework assignments in each group CC & CC+C, and 2) attendance/adherence to scheduled appointments. Other treatment implementation notes that do not directly impact human subjects protections include interventionists notes about "Process Considerations and Interventionist Pressures" including the interventionists' opinions about the two interventions (CC and CC+C).

18. Differentiation of "usual (standard) care" from research activities.

All procedures listed are voluntary in nature and unrelated to current clinical care. Participation in a similar clinical pilot program may be available to some families (e.g., those who live in rural areas may qualify for the Telephone Assisted Dementia Outreach Program, pending sustainment and availability which is unknown at the time this protocol is being submitted). However, no permanent services or "usual" treatment options similar to the one being studied are available at the Tuscaloosa VAMC.

19. Enlisting clinical expertise.

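### Nothing in the plan masks the research assistant who interviews veterans at 6 months, and a small assessor bias could reach the plan's effect threshold

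*Combined protocol and SAP*

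**What the plan says.** **Who collects the data.** Section 17 (Baseline, 6-month, and 12-month Assessments) gives the veteran's data to a research assistant: "Patient data will be collected interview-style by a trained assessor (research assistant) for the veteran with dementia". Caregiver forms are handled differently: "while the caregiver measures will be completed independently (paper and pencil".

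**When arm becomes known.** The end of the Measures list in section 17 states: "Once baseline data are collected, dyads will be randomly assigned to a condition". Arm does not exist at baseline, so only the follow-up assessments can be influenced by it.

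**How the outcomes are obtained.** Item g of Measures describes the CSDD as a scale "which relies on an interview with the individual and the caregiver will be used to assess depressive and anxiety symptoms". It does not say who assigns the score. Table 1 lists "Social Engagement (V, CG" (with an asterisk on CG), and its note reads "V = measures completed by veteran; CG = completed by caregiver".

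**Who delivers treatment.** Section 17 (Treatment delivery) names a different role: "The MSW-level interventionist will be trained to criterion and will be certified before administering the intervention". The fidelity checklist there asks the interventionist whether the other arm would have suited the dyad better. There is no corresponding item for the outcome assessor.

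**What is expected.** Section 6 predicts: "6 month gains in shared pleasant events, social engagement, and quality of life will also be greater in CC+C than in CC alone". For depressive symptoms it predicts improvement from baseline in both groups, with no difference between them.

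**How results are read.** Section 20 compares arms at 6 months by ANCOVA adjusted for baseline. It uses partial eta squared as its main gauge and treats a between-arm value of .01 or more as possibly of clinical importance.

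**The concern.** An interviewer who knows the arm can prompt, interpret or record answers differently without meaning to. The risk is greater here because section 14 admits veterans whose cognition ranges from intact to severely impaired, so the interviewer's help and interpretation count for more. Section 6 also gives a study-team assessor a stated direction to expect on social engagement and quality of life.

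The plan recognises expectation bias in the person delivering treatment but makes no provision for it in the person collecting outcomes. Followed as written, it would allow an assessor who knows the arm to conduct the 6-month veteran interviews. Section 32 says that the results will serve as pilot data for later grant proposals, so a false signal would carry forward.

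**Working it through.** The documents give no figure for assessor bias. The power inputs sit in grant text that is not part of the document, so there is no plan figure to reproduce. The check has three steps.

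**1. Which 6-month outcomes this route reaches** (Table 1 read with the data-collection sentence in section 17)

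| Outcome | Source | Reached? |
|---|---|---|
| CSDD | Veteran and caregiver; interview-based (item g) | Yes; scorer not stated |
| Social engagement, QOL-AD, EQ-5D | Veteran, plus caregiver proxy | Veteran part only, through influence on answers |
| Dyadic adjustment, mutuality, FFMQ, subjective stress and health | Veteran and caregiver, each for self | Veteran part only |
| Caregiver burden, GAD-7, CES-D, WHO-QOL-OLD, desire to institutionalize | Caregiver, on paper | No |
| Nursing home placement | Caregiver or health record | No |

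**2. The threshold on a standardised scale**

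For two equal arms, with d in units of the ANCOVA residual SD:

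- partial eta squared = d² / (d² + 4)
- d = 2 × √(eta² / (1 − eta²))

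The plan's threshold: 2 × √(.01 / .99) = 0.201.

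Assumed assessor shifts, with no true effect:

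- 0.1 SD: 0.01 / 4.01 = .0025
- 0.2 SD: 0.04 / 4.04 = .0099
- 0.3 SD: 0.09 / 4.09 = .0220

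A shift of about 0.2 residual SD is therefore the same size as the smallest effect to which the plan gives weight.

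**3. Chance of reaching .01 in favour of CC+C with no true effect**

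Inputs: 50 completers (section 20); 25 per arm (equal allocation assumed); one covariate, so residual df = 50 − 3 = 47.

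- Critical F = (.01 / .99) × 47 = 0.475, so critical t = 0.689
- Noncentrality = shift × √(25 × 25 / 50) = shift × 3.536

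| Assumed shift (residual SD) | Noncentrality | Chance of .01 or more favouring CC+C |
|---|---|---|
| 0 | 0 | 25% |
| 0.1 | 0.354 | 37% |
| 0.2 | 0.707 | 51% |
| 0.3 | 1.061 | 65% |

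The first row matters. With no bias and no effect, sampling noise alone passes .01 in favour of CC+C a quarter of the time, and in one direction or the other 49% of the time. That weakness belongs to the threshold and is a separate issue. The effect attributable to the assessor is the rise from 25%.

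**The case against.** The strongest reply is that silence is not evidence of an unmasked assessor. The plan already names separate roles for assessment and treatment, and both arms receive active telephone care, so arm may be less obvious than against an untreated control. This stands in part. A reader might infer that the research assistant is unmasked, but the documents say neither that nor the opposite. What they support is that no provision for masking exists.

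Three further limits stand:

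- **Engagement is not described as rater-scored.** A reader might infer this from the interview format. Table 1 lists it as completed by veteran and caregiver, and section 20 plans veteran self-report and caregiver proxy analyses with no assessor-rated family. Masking would address influence on the veteran's answers but not the caregiver's proxy report.
- **The mood direction is weak.** A reader might infer that CSDD scores would lean towards CC+C. Section 6 predicts no such advantage for depressive symptoms, and the documents do not say that the interviewer scores the CSDD.
- **Reach is partial.** Section 12 allows veteran interviews to be discontinued for severe impairment, and section 10 lets caregivers take part alone. Fewer than 50 veterans may be interviewed.

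It is also fair to say that 0.2 SD is simply the .01 threshold re-expressed, and that no document figure supports a bias of that size. The calculation shows how sensitive the reading is to bias, not how large any bias would be.

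**Conclusion.** The point holds as a gap in the conduct of outcome assessment. Veteran outcomes are collected by interview after randomisation, nothing keeps the assessor from knowing the arm, and the effect threshold is low enough for a small bias to matter. It is confined to the CSDD and the veteran-reported measures, most clearly those for which section 6 predicts an advantage for CC+C, such as social engagement and quality of life.

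Under equal allocation and 50 completers, an assumed shift of 0.2 residual SD would by itself match the threshold and would roughly double the chance of a signal favouring CC+C, from 25% to 51%. The 0.1 to 0.3 SD range is an assumption, and the documents establish neither the size nor the direction of any actual bias. This is a cheap improvement; it does not show that the results would be biased.

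**What to change.** Add to section 17:

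- The research assistant who carries out follow-up veteran assessments (6 months, and 12 months where the veteran is interviewed) is not the interventionist and has no access to allocation, session records or the CCIS.
- Dyads are asked before each follow-up assessment not to mention their sessions.
- The person who scores the CSDD is named by role.
- After each 6-month visit the assessor records a guess of arm and any unmasking.

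If masking cannot be kept, say so and report it as a limitation on the interview-collected veteran outcomes.

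The cost is wording, one extra item per visit and access control. Section 26 already limits the CCIS to verified users confirmed by the principal investigator. The downside is that tasks that reveal arm must sit with other existing team members. Section 20 has the research assistant review all data for accuracy and complete tracking forms, so that work may need to be divided; section 27(d) mentions a research coordinator or Health Science Specialist. Some unmasking will still occur because dyads may disclose their arm, which is why the guess should be recorded.
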